8.4.2 Method of detecting AEs and SAEs

Care will be taken not to introduce bias when detecting AEs and/or SAEs. Open-ended and nonleading verbal questioning of the participant is the preferred method to inquire about AE occurrences.

8.4.3 Follow up of AEs and SAEs

After the initial AE/SAE report, the investigator is required to proactively follow each study participant at subsequent visits/contacts. All AEs, and SAEs, will be followed until resolution, stabilization, the investigator determines that it is no longer clinically significant, the event is

otherwise explained, or the study participant is lost to follow up (as defined in Section 7.3). Further information on follow-up procedures is given in Appendix 3 (Section 10.3).

8.4.4 Regulatory reporting requirements for SAEs

Prompt notification of an SAE by the investigator to the sponsor is essential so that legal obligations and ethical responsibilities towards the safety of participants and the safety of a study intervention under clinical investigation are met.

Further to the reporting of an SAE from the investigator to the sponsor, an expectedness assessment will be made per the IB, as reference safety information for this study, and relevant sponsor's SOPs, and appropriate reporting of suspected unexpected serious adverse reactions (SUSARs) will be carried out to health authorities as per International Council for Harmonisation (ICH) and local regulatory requirements. Investigator safety reports must be prepared for SUSARs according to local regulatory requirements and sponsor policy and forwarded to investigators as necessary.

The sponsor has a legal responsibility to notify both the local regulatory authority and other regulatory agencies about the safety of a study intervention under clinical investigation. The sponsor will comply with country-specific regulatory requirements relating to safety reporting to the regulatory authority, Institutional Review Boards (IRB)/Independent Ethics Committees (IEC), and investigators.

An investigator who receives an investigator safety report describing an SAE or other specific safety information (eg, summary or listing of SAEs) from the sponsor will review and then file it along with the IB and will notify the IRB/IEC, if appropriate according to local requirements.

8.4.5 Pregnancy

Details of all pregnancies in female study participants and, if consented, in female partners of male study participants will be collected after the start of study intervention and, until at least 12 months after the delivery date.

If a pregnancy is reported, the investigator will record pregnancy information on the appropriate form and submit it to the sponsor within 24 hours of learning of the pregnancy, and should follow the procedures outlined in Appendix 4 (Section 10.4).

While pregnancy itself is not considered to be an AE, any pregnancy will need to be reported. In some circumstances, a pregnancy report is considered as an SAE: miscarriage, elective abortion when medically indicated (eg, when pregnancy is endangering life or health of woman or when fetus will be born with severe abnormalities), unintended pregnancy after hormonal contraceptive failure (if the hormonal contraceptive was correctly used), ectopic pregnancy, fetal demise, or any congenital anomaly/birth defect of the baby.

The participant/pregnant female partner will be followed to determine the outcome of the pregnancy. The investigator will collect follow-up information on the participant/pregnant female partner and the neonate, and the information will be forwarded to the sponsor.

Any poststudy pregnancy-related SAE in either the mother or the neonate considered reasonably related to the study intervention by the investigator will be reported to the sponsor as described in Section 8.4.4. While the investigator is not obligated to actively seek this information in

former study participants/pregnant female partner, he or she may learn of an SAE through spontaneous reporting.

Any female participant who becomes pregnant while participating in the study will discontinue study intervention and return for an ETV as described in the Schedule of Activities (Section 1.3).

If the study participant decides to completely withdraw from the study, an SFU visit should be scheduled 5 to 9 days after the final dose of study intervention.

The investigator must inform the participant of any known potential risks the study intervention may have to the mother and/or the developing fetus/infant as well as any available treatment alternatives.

The investigator should discuss with the participant the possibility of continuing study participation by attending the scheduled visits for assessments as their condition allows but without the participant continuing study intervention. Protocol-specified blood sample collection will be adapted as indicated in the Schedule of Activities (Section 1.3) considering the study participant's condition during the study. The tests or assessments that are considered contraindicated during the pregnancy should not be performed. Caution is required with respect to concomitant medication if not contraindicated in pregnancy. As indicated, investigators are advised to discuss the case with the sponsor study physician to gain feedback on protocol-defined actions.

8.4.6 Adverse events of special interest

An adverse event of special interest (AESI) is any AE that a regulatory authority has mandated be reported on an expedited basis, regardless of the seriousness, expectedness, or relatedness of the AE to the administration of a UCB product/compound or associated medical device. For minzasolmin, the following events require immediate reporting (within 24 hours regardless of seriousness) to UCB:

- Possible Hy's Law (as per Section 7.1.1)
 - Potential Hy's Law, defined as $\geq 3 \times \text{ULN}$, ALT or AST with coexisting $\geq 2 \times \text{ULN}$ total bilirubin in the absence of $\geq 2 \times \text{ULN}$ ALP, with no alternative explanation for the biochemical abnormality (ie, without waiting for any additional etiologic investigations to have been concluded). Follow up information should be reported if an alternative etiology is identified during investigation and monitoring of the participant.

- Hypersensitivity reactions (such as rash, angioedema, or anaphylaxis)

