Other screening tests	
Total immunoglobulin E testUrine alcohol and cotinine testFollicle stimulating hormone and estradiol (females only)Urine drug screen (to include at minimum: amphetamines, barbiturates, cocaine, opiates, cannabinoids, and benzodiazepines, creatinine [to exclude dilution of urine samples])Serology (HIV antibody, HBsAg, HCV-Ab, and HBcAb [IgG and IgM]) 
The results of each test must be entered into ClinBase.

ALP=alkaline phosphatase; ALT=alanine aminotransferase; aPTT=activated partial prothrombin time; AST=aspartate aminotransferase; HBcAb=hepatitis B core antibody; HBsAg=hepatitis B surface antigen; HCV-Ab=hepatitis C virus antibody; HIV=human immunodeficiency virus; IgG=immunoglobulin G; IgM=immunoglobulin M; INR=international normalized ratio; PT=prothrombin time; RBC=red blood cell; ULN=upper limit of normal; WBC=white blood cell

^aBlood hematology and chemistry laboratory tests will be obtained in the fasting state following an overnight fast of at least 10 hours.

^bDetails of liver chemistry stopping criteria and required actions and follow up are given in Section 7.1.1 and Section 10.6. All events of ALT [or AST] $\geq 3 \times$ ULN and bilirubin $\geq 2 \times$ ULN ($>35\%$ direct bilirubin) or ALT [or AST] $\geq 3 \times$ ULN and INR >1.5 , (if INR measured) which may indicate severe liver injury (possible Hy's Law), must be reported to UCB in an expedited manner (excluding studies of hepatic impairment or cirrhosis).

^cThe following parameters are part of hepatic function testing: ALP, ALT, AST, and bilirubin.

^dIf ALP is elevated, consider fractionating.

^eEstimated glomerular filtration rate, based on the Chronic Kidney Disease Epidemiology Collaboration 2021 equation, only at screening.

Investigators must document their review of each laboratory safety report.

10.3 Appendix 3: Adverse events – Definitions and procedures for recording, evaluating, follow up, and reporting

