
ALT-absolute
 
ALT \geq3xULN If ALT \geq3xULN AND bilirubin \geq2xULN ($>35\%$ direct bilirubin) or INR >1.5, report as a SAE^{ab} See additional actions and follow-up assessments below
	
• Immediately discontinue study intervention• Report the event to the sponsor within 24 hours• Complete ClinBase, and complete an SAE data collection tool if the event also met the criteria for an SAE^b• Perform liver function follow-up assessments• Monitor the participant until liver function test abnormalities resolve, stabilize, or return to baseline (see MONITORING)• Consider the need for a toxicology screening. 
• Viral hepatitis serology^c• Obtain INR and recheck with each liver chemistry assessment until the transaminases values show downward trend• Obtain blood sample for PK analysis at predose and at 0.5, 1, 1.5, 2, 4, 8, 12, 24, 36, 48, 72, and 96 hours after minzasolmin administration^d• CPK and LDH• Fractionate bilirubin, if total bilirubin \geq 2xULN

Table 10-3: Phase 1 liver chemistry stopping criteria and follow up assessments table

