^a Serum bilirubin fractionation should be performed if testing is available. If serum bilirubin fractionation is not immediately available, discontinue study intervention if ALT \geq 3xULN and bilirubin \geq 2xULN. Additionally, if serum bilirubin fractionation testing is unavailable, **record the absence/presence of detectable urinary bilirubin on dipstick** which is indicative of direct bilirubin elevations suggesting liver injury.

^b All events of ALT \geq 3xULN and bilirubin \geq 2xULN ($>35\%$ direct bilirubin) or ALT \geq 3xULN and INR >1.5 may indicate severe liver injury (**possible 'Hy's Law'**) and **must be reported as an SAE (excluding studies of hepatic impairment or cirrhosis)**. The INR measurement is not required and the stated threshold value will not apply to participants receiving anticoagulants.

^c Includes: Hepatitis A IgM antibody; HBsAg and HBcAb; hepatitis C RNA; cytomegalovirus IgM antibody; Epstein-Barr viral capsid antigen IgM antibody (or if unavailable, heterophile antibody or monospot testing); and hepatitis E IgM antibody.

^d PK sample may not be required for participants known to be receiving placebo or noncomparator interventions. Record the date/time of the PK blood sample draw and the date/time of the final dose of study intervention before the PK blood sample draw. If the date or time of the final dose is unclear, provide the participant's best approximation. If the date/time of the final cannot be approximated OR a PK sample cannot be collected in the

Table 10–3: Phase 1 liver chemistry stopping criteria and follow up assessments table

time period indicated above, do not obtain a PK sample. Instructions for sample handling and shipping are in the Study Reference Manual.

This document cannot be used to support any marketing application and any extensions or variations thereof.
PUBLIC COPY

10.7

Appendix 7: Device adverse events (AEs), adverse device effects (ADEs), serious adverse events (SAEs), and device deficiencies: Definition and procedures for recording, evaluating, follow-up, and reporting

Not applicable.

This document cannot be used to support any marketing authorization application and any extensions or variations thereof.

PUBLIC COPY

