6.1.7 AEs of Special Interest

AE of special interest are:

- Possible Hy's Law: Potential Hy's Law is defined as $\geq 3 \times \text{ULN}$, ALT or AST with coexisting $\geq 2 \times \text{ULN}$ total bilirubin in the absence of $\geq 2 \times \text{ULN}$ ALP, with no alternative explanation for the biochemical abnormality (ie, without waiting for any additional etiologic investigations to have been concluded).
- Hypersensitivity reactions (such as rash, angioedema, or anaphylaxis).

A listing will be produced of Potential Hy's Law for the SS by formulation and feeding condition.

A listing will be produced for Hypersensitivity reactions for the SS by formulation and feeding condition group using the following search strategy: Standardized MedDRA Queries (SMQ)='Hypersensitivity' (Broad) AND SMQ=Anaphylactic reaction (Broad).

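### The protocol uses the label possible Hy's Law for three non-identical criteria, and the SAP's AESI listing follows one that leaves out some cases the protocol requires to be reported as SAEs

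*Protocol*

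**What the plan says.** Three places in the current protocol describe possible or potential Hy's Law.

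- **Protocol 8.4.6 (AESI).** The bullet opens "Possible Hy's Law (as per Section 7.1.1" and then defines the event: ALT or AST at least 3×ULN, total bilirubin at least 2×ULN, ALP not at or above 2×ULN, and "with no alternative explanation for the biochemical abnormality (ie, without waiting for any additional etiologic investigations to have been concluded". Reporting is within 24 hours regardless of seriousness.
- **Protocol Table 10-1, footnote b.** ALT or AST at least 3×ULN with bilirubin at least 2×ULN (more than 35% direct), or with INR above 1.5 if measured. The footnote says of these events: "which may indicate severe liver injury (possible Hy's Law), must be reported to UCB in an expedited manner".
- **Protocol Table 10-3 and its footnote b (Appendix 6).** ALT at least 3×ULN with bilirubin at least 2×ULN (more than 35% direct) "or INR >1.5, report as a SAE". Footnote b repeats both arms (for the second, ALT at least 3×ULN "and INR >1.5 may indicate severe liver injury"), applies the possible Hy's Law label and makes SAE reporting mandatory.

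SAP 6.1.7 restates the Section 8.4.6 criterion without the reference to Section 7.1.1, and then says: "A listing will be produced of Potential Hy's Law for the SS by formulation and feeding condition". SAP 5.5.2 says the adverse event listing will flag TEAEs, serious TEAEs and AESIs.

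**The concern.** One label carries three sets of conditions and three reporting consequences: AESI, expedited report and SAE. The same laboratory result can therefore be possible Hy's Law under one section and not under another. The SAP builds its only dedicated liver output on the Section 8.4.6 criterion, which has an ALP exclusion and no INR arm. A case that Appendix 6 requires to be reported as an SAE, under the possible Hy's Law name, can then be absent from the listing titled Potential Hy's Law and carry no AESI flag.

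Hepatic effects are a monitored risk in this programme. Protocol Section 2.3 reports 8 transaminase elevations above 3×ULN among 496 Phase 2 participants (8/496 = 1.6%), 2 of them above 10×ULN.

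**Working it through.** **Step 1: conditions side by side.** The plan gives no figure to reproduce here, because the point concerns definitions.

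| Condition | 8.4.6 and SAP 6.1.7 (criterion 1) | Table 10-1 fn b (criterion 2) | Table 10-3 and fn b (criterion 3) |
|---|---|---|---|
| Transaminase ≥3×ULN | ALT or AST | ALT or AST | ALT only |
| Bilirubin ≥2×ULN | total, any direct fraction | >35% direct | >35% direct |
| INR >1.5 as alternative to bilirubin | no | yes, if measured | yes |
| ALP ≥2×ULN excludes the case | yes | no | no |
| No alternative explanation required | yes | no | no |
| Consequence | AESI | expedited report | SAE |

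**Step 2: enumeration.** Take six yes/no results: ALT ≥3×ULN, AST ≥3×ULN, bilirubin ≥2×ULN, direct fraction >35% (counted only if bilirubin is ≥2×ULN), ALP ≥2×ULN and INR >1.5. Bilirubin and direct fraction together have 3 states, so there are 2 × 2 × 3 × 2 × 2 = 48 patterns. The no-alternative-explanation clause is taken as met, which favours inclusion under criterion 1.

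- Criterion 1: 3 transaminase states × 2 direct-fraction states × 1 ALP state × 2 INR states = 12.
- Criterion 2: 3 transaminase states × 4 bilirubin/INR states × 2 ALP states = 24.
- Criterion 3: 2 transaminase states × 4 bilirubin/INR states × 2 ALP states = 16.
- Both 1 and 3: 2 transaminase states × 3 bilirubin/INR states × 1 ALP state = 6.
- SAE under criterion 3 but outside criterion 1: 16 − 6 = 10. Four of these have INR >1.5 with bilirubin <2×ULN (two of the four also have ALP ≥2×ULN). The other six have bilirubin ≥2×ULN with ALP ≥2×ULN.
- Criterion 1 but not criterion 3: 12 − 6 = 6. Four are AST-only rises. Two have a direct fraction of 35% or less without INR >1.5.

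These counts show logical mismatch. They are not event frequencies.

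**Step 3: concrete cases.**

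| Result (×ULN, except INR) | Criterion 1 | Criterion 2 | Criterion 3 |
|---|---|---|---|
| ALT 4, INR 1.6, normal bilirubin | no | expedited | SAE |
| ALT 4, bilirubin 2.5 (>35% direct), ALP 2.5 | no | expedited | SAE |
| AST 4, ALT <3, bilirubin 2.5 (>35% direct), normal ALP, INR not raised | AESI | expedited | no |

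**Step 4: can the INR arm be triggered?** INR is listed under clinical chemistry in Table 10-1, and Table 10-3 orders it once ALT reaches 3×ULN. Schedule of Activities footnote e limits Days 5 and 10 to hepatic function tests, which Table 10-1 footnote c defines as ALP, ALT, AST and bilirubin. After dosing starts, routine INR is therefore expected only with the Day 15 and follow-up laboratory panels.

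**Step 5: what other outputs would show the case?** SAP 5.5.2 ends treatment emergence 4 days after the last treatment. The last dose is on Day 11, and 11 + 4 = 15. SAP Table 4 places follow-up on Days 16 to 20, so an event with onset there is post-treatment and is kept out of every tabulated summary. It stays in the all-AE listing. On the SAP's description, however, that listing flags serious TEAEs, not all SAEs, so a case outside criterion 1 would carry neither the serious TEAE flag nor the AESI flag. SAP 6.1.8 sets no clinically significant laboratory criteria, and SAP Table 11 does not include INR.

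**The case against.** The strongest reply is that there is only one AESI definition. Section 8.4.6 states it and SAP 6.1.7 repeats it; the other two passages govern expedited reporting and liver follow-up. On that view an SAE outside the AESI definition is not missing from an AESI listing. It is right that protocol and SAP agree on the AESI criterion. It does not explain why two other passages give the same name to different criteria, or why the AESI bullet refers the reader to the liver stopping section.

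Several stronger readings are tempting, and the documents do not support them.

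- *A reader might infer that the sponsor may not be told.* Table 10-3 requires notification within 24 hours for any ALT of 3×ULN or more. The AST-only pattern is reportable under Section 8.4.6 and Table 10-1 footnote b.
- *A reader might infer that events vanish from the report.* They remain in the all-AE listing and, if treatment-emergent, in the serious TEAE table. The exception is in tabulation and flagging for onset after Day 15.
- *A reader might take the Section 7.1.1 reference to mean the Table 10-3 criterion.* This cannot be shown. The criteria of Section 7.1.1 are in Figure 7-1, which is not available in the text reviewed. Its abbreviation list includes AST as well as INR, and the section cites Appendix 6 for assessments and follow-up actions.
- *A reader might count a Gilbert's syndrome case* (for example ALT 4×ULN, bilirubin 2.2×ULN with 20% direct) as an AESI under Section 8.4.6 alone. That depends on whether the recorded diagnosis counts as an alternative explanation, which the documents do not settle.

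The programme figures also need context. The 8 of 496 arose under daily dosing for 18 months, mostly 2 to 3 months after the first dose; none had raised bilirubin or INR, and none met Hy's law.

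**Conclusion.** The concern holds as an internal contradiction in how possible Hy's Law is classified. Ten of the 16 logical patterns that Table 10-3 makes SAEs lie outside the criterion behind the SAP's AESI listing and flag, and 6 of that criterion's 12 patterns are not SAEs under Table 10-3. The practical weight is greatest for onset at follow-up, where the serious TEAE tables do not catch the case either.

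The effect is on SAE/AESI classification and on reporting outputs. It does not reach the primary PK analysis. Few or no such events are expected in 18 healthy participants given three single doses, with ALT, AST or ALP above ULN excluded at entry. The conclusion rests on the written text of Section 8.4.6, Tables 10-1 and 10-3 and SAP 6.1.7, and does not depend on the content of Figure 7-1. It is worth correcting because the correction is cheap, not because events are likely.

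**What to change.** The sponsor should reconcile Sections 7.1.1 and 10.6, Section 8.4.6 and Table 10-1 footnote b. Its medical team decides the criterion, and this review proposes none. State it once, refer to it from the other places, and carry the reconciled wording into SAP 6.1.7.

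Unless and until that is done, the SAP listing should include every participant who meets any of the current criteria, whatever the onset relative to the last dose. It should show ALT, AST, ALP, total and direct bilirubin, and INR where measured, with a note that Days 5 and 10 have no routine INR. Once the passages are reconciled, the broader listing can be narrowed to the single criterion.

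The cost is protocol wording and one wider listing. All the analytes are already in Table 10-1, so no added sampling is needed.

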8.4.6.1 Hypersensitivity reaction monitoring and management

If a study participant experiences a hypersensitivity reaction (such as rash, angioedema, or anaphylaxis), he or she will contact the clinical site immediately (24 hours a day) or seek urgent medical advice in accordance with instructions from the investigator.

The advice will be based on the clinical presentation and may be to present to the clinical site or seek medical attention in the community.

The study participant should be rapidly and thoroughly assessed in line with the actions below.

Hypersensitivity reactions will be AESIs and require expedited reporting to UCB, regardless of seriousness, expectedness, or relatedness in line with Section 8.4.6. This will allow for rapid evaluation.

Procedures for the management of minzasolmin are provided in Appendix 3 (Section 10.3).

8.4.6.1.1 Medical History

Detailed history of the hypersensitivity reaction (eg, rash, angioedema, or anaphylaxis) with onset time of symptoms and signs, location of symptoms and signs, first appearance, its evolution (eg, where the rash appeared and to where it spread), any other symptoms (eg, pruritus, swelling, breathlessness), especially if showing a systemic involvement (anaphylaxis), will be recorded. The criteria for anaphylaxis are described in Section 8.4.6.1.1.1.

The clinical progression of the hypersensitivity reactions symptoms should be recorded and any change in symptoms or severity should also be recorded together with the timing.

All AEs reported concurrently should be included within the review.

It will also be important to investigate any recent intake of new medications, herbs, supplements, or the recent use of any topical substances.

8.4.6.1.1.1 Anaphylaxis

Sampson et al. listed criteria for the diagnosis of anaphylaxis. This was developed at the Second National Institute of Allergy and Infectious Disease/Food Allergy and Anaphylaxis Network symposium (Sampson et al, 2006).

Acute onset=minutes to a few hours.

Criteria for diagnosis include 1 or more of the following:

- Acute onset of an illness with symptom complex 1 (see below)
- Acute onset of symptom complex 2 (see below) after exposure to a likely allergen
- Acute onset of a reduced SBP after exposure to a known allergen for the participant

Symptom complex 1 is indicated by both of the following:

- At least 1 of the following:
 - Skin involvement (generalized hives, pruritis, flushing)
 - Mucous membrane involvement (swollen lips, swollen tongue, swollen uvula)
- At least 1 of the following:
 - Respiratory compromise (dyspnea, wheezing, bronchospasm, stridor, reduced peak expiratory flow, hypoxemia)
 - Reduced SBP, collapse, syncope, incontinence or other symptom of end-organ dysfunction

Symptom complex 2 is indicated by 2 or more of the following:

- Skin or mucous membranes (as above)

- Respiratory compromise (as above)
- Reduced BP (as above)
- Persistent GI tract symptoms (cramping, abdominal pain, vomiting)

Reduced SBP is indicated by 1 of the following:

- BP <70% of Baseline SBP

Limitations:

Treudler et al. found that the criteria may not perform as well as others for the recognition of severe, immediate reactions (Treudler et al, 2008).

